7.1. Screening

7.1.1. Within 28 days prior to registration for protocol therapy:

- Screen for the eligibility for the trial. Patient must satisfy all the inclusion criteria and must not have any exclusion criterion.
- Informed consent
- Diagnosis and staging: pathology report and TNM staging.
- Medical history
- Physical exam and ECOG PS
- Vital signs: temperature, blood pressure, pulse rate, respiratory rate, weight, and height (screen only).
- 12-lead ECG (in triplicate, 2-5 minutes apart). All 12-lead ECGs should be obtained after the subject has been resting in a supine position for at least 5 minutes in each case.
- Complete blood count with differential (CBC): to include hemoglobin, platelet count, red blood cell count, total white cell count.
- Comprehensive metabolic panel (CMP): to include albumin, alkaline phosphatase, alanine aminotransferase, aspartate aminotransferase, bicarbonate, calcium, chloride, creatinine, gamma glutamyl transferase (GGT), glucose, lactate dehydrogenase, magnesium, potassium, sodium, total bilirubin, total protein, urea or blood urea nitrogen (depending on local practice), uric acid. If total bilirubin is ≥2xULN (and no evidence of Gilbert's syndrome), fractionate into direct and indirect bilirubin. GGT at baseline and as clinically indicated.
- Amylase and lipase
- Urinalysis: to include bilirubin, blood, glucose, ketones, pH, protein, and specific gravity. Microscopy should be used as appropriate to investigate white blood cells and use the high power field for red blood cells.
- Thyroid stimulating hormone. Free T3 and free T4 will only be measured if TSH is abnormal.
- Prothrombin time, aPTT and INR
- Calculated creatinine clearance using the Cockcroft-Gault formula or by 24-hour urine collection for determination of creatinine clearance.
- [Within 14 days of registration] Serum pregnancy test for women of childbearing potential (WOCP)
- Baseline signs and symptoms; concomitant medications.
- Baseline CT scan of chest, abdomen and pelvis

7.2. On Treatment

7.2.1. Cycle 1 Day 1 (or within 3 days prior):

- Physical exam and ECOG PS, weight
- Vital signs: blood pressure and pulse rate will be measured before, during and after the infusion at the following times (based on a 60-minute infusion):
 - 1. At the beginning of the infusion (at 0 minutes \pm 5 minutes)
 - 2. at 30 minutes after the start of infusion (\pm 5 minutes),
 - 3. at the end of infusion (at 60 minutes \pm 5 minutes)

- 4. at 30 minutes post-infusion (90 minutes from the start of the infusion \pm 5 minutes)
- 5. at 60 minutes post-infusion (120 minutes from the start of the infusion \pm 5 minutes)
- The 1-hour post-infusion observation period will apply to the first infusion only and then for subsequent infusions as clinically indicated.
- If the infusion takes longer than 60 minutes, blood pressure and pulse measurements should follow the principles described here (e.g. every 30 minutes), or more frequently if clinically indicated.
- ECG within an hour prior to start of infusion and at least one time point 0 to 3 hours after the infusion. ECGs recorded during the treatment phase will be single tracing. The same method of assessment should be used throughout the study. Twelve-lead ECGs will be obtained after the subject has been resting in a supine position for at least 5 minutes in each case.
- Complete blood count with differential (CBC)
- Comprehensive metabolic panel (CMP)
- Amylase and/or lipase (depending on local practice)
- Urinalysis
- Durvalumab administration
- Correlative studies:
 - CTC blood sample optional (pre-dose) (collected only on subjects enrolled at Indiana University)
 - Whole blood- optional
 - Archived tissue samples from diagnosis and surgery (mandatory, if available)
- Banking studies:
 - Whole blood- optional
 - Unstained slides from archived tumor blocks from diagnosis and surgery (optional, if available)
 - Serum and plasma- optional

Notes: Cycle 1 Day 1 lab testing need not be repeated if completed within 7 days of starting protocol therapy.

See CLM for collection, processing, labeling and shipping instructions.

7.2.2. Cycle 2+ Day 1 (±3 days):

- Physical exam and ECOG PS, weight
- Vital signs: blood pressure and pulse rate will be measured before, during and after the infusion at the following times (based on a 60-minute infusion):
 - 1. At the beginning of the infusion (at 0 minutes \pm 5 minutes)
 - 2. at 30 minutes after the start of infusion (\pm 5 minutes),
 - 3. at the end of infusion (at 60 minutes \pm 5 minutes)
 - If the infusion takes longer than 60 minutes, blood pressure and pulse measurements should follow the principles described here (e.g. every 30 minutes), or more frequently if clinically indicated.
- Complete blood count with differential (CBC)
- Comprehensive metabolic panel (CMP)
- Amylase and/or lipase (depending on local practice)

- Urinalysis
- Adverse events, immune-related adverse events, adverse events of special interest and concomitant medications
- Durvalumab administration
- Every 3 months (prior to Cycle 4, 7, 10, etc.): CT of chest, abdomen and pelvis
- Cycle 4 Day 1: (in addition to procedures listed above)
 - ECG within an hour prior to start of infusion and at least one time point 0 to 3 hours after the infusion. ECGs recorded during the treatment phase will be single tracing. The same method of assessment should be used throughout the study. Twelve-lead ECGs will be obtained after the subject has been resting in a supine position for at least 5 minutes in each case.
 - Pre-dose C4D1 Correlative studies:
 - CTC blood sample optional (pre-dose) (collected only on subjects enrolled at Indiana University)

7.3. Protocol therapy discontinuation

A subject will be discontinued from the protocol therapy under the following circumstances:

- Grade \geq 3 infusion reaction
- If there is clear evidence of disease relapse (per RECIST 1.1). NOTE: If pseudoprogression is suspected, a subject will be allowed to continue durvalumab until biopsy or repeat radiographic scans confirm disease relapse.
- If the treating physician thinks a change of therapy would be in the best interest of the subject
- If the subject requests to discontinue protocol therapy
- If the protocol therapy exhibits unacceptable toxicity
- If a female subject becomes pregnant
- If protocol therapy is interrupted for \geq 42 days due to a treatment-related adverse event.

7.4. Safety Follow-up: 30 days (±7 days) after last dose of protocol therapy

Subjects discontinued from the treatment phase of the study for any reason will be evaluated 30 days (\pm 7) after the last dose of study drug or as soon as possible thereafter (ex. protocol therapy interruption for \geq 42 days). If a subject is discontinued due to disease relapse, the subject will be off study after the Safety Follow-up visit and no further follow up will be performed.

- Physical exam and ECOG PS
- Vital signs: temperature, blood pressure, pulse rate, respiratory rate and weight
- 12-lead ECG. ECG should be obtained after the subject has been resting in a supine position for at least 5 minutes. The same method of assessment should be used throughout the study.
- Complete blood count with differential (CBC)
- Comprehensive metabolic panel (CMP)
- Urinalysis
- Adverse events, immune-related adverse events, adverse events of special interest and concomitant medications
- Banking studies:
 - Serum and plasma- optional

7.5. At Recurrence:

- Correlative studies:
 - CTC blood sample optional (collected only on subjects enrolled at Indiana University) at the time of disease recurrence during treatment or follow up.

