3. ELIGIBILITY CRITERIA

3.1.Inclusion Criteria

Subject must meet all of the following applicable inclusion criteria to participate in this study:

3.1.1 Written informed consent and HIPAA authorization for release of protected health information obtained from the subject prior to performing any protocol-related procedures, including screening evaluations.
 NOTE: HIPAA authorization may be included in the informed consent or obtained

NOTE: HIPAA authorization may be included in the informed consent or obtained separately.

- **3.1.2** Age \geq 18 years at the time of consent.
- **3.1.3** ECOG Performance Status of 0-1 within 28 days prior to registration for protocol therapy.
- **3.1.4** Females of childbearing potential and males must be willing to use two effective methods of contraception (See section 5.5.1) from the time consent is signed until 3 months after treatment discontinuation.
- **3.1.5** Females of childbearing potential must have a negative serum pregnancy test within 14 days prior to registration for protocol therapy.

NOTE: Female subjects are considered of childbearing potential unless they are surgically sterile (they have undergone a hysterectomy, bilateral tubal ligation, or bilateral oophorectomy) or they are ≥ 60 years old and naturally postmenopausal for at least 12 consecutive months. See section 5.5.1.

- 3.1.6 Histological evidence of persistent residual esophageal adenocarcinoma including gastroesophageal junction adenocarcinoma following definitive concurrent chemoradiotherapy (carboplatin and paclitaxel or cisplatin and 5-FU) in the surgical sample (esophagus or lymph node or both) obtained at the time of esophagectomy.
 NOTE: Persistent residual disease is defined as follows (modified from College of American Pathologists Guidelines):
 - No residual tumor (Grade 0, complete response, 0% tumor). This group will not be included in this study.
 - Marked response (Grade 1, 0-<10% residual tumor)
 - Moderate response (Grade 2, 10-50% residual tumor)
 - No definite response (Grade 3, >50% residual tumor)
- **3.1.7** Minimum of 1 month and maximum of 3 months from surgical resection with no evidence of disease progression at the time of enrollment.
- 3.1.8 Must have adequately recovered from surgery as judged by the treating investigator.
- **3.1.9** Laboratory values must be obtained within 28 days prior to registration for protocol therapy.

- White blood cell count (WBC) \geq 3 K/mm³

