4. SUBJECT REGISTRATION

All subjects must be registered and randomized through Big Ten CRC Administrative Headquarters' electronic data capture (EDC) system. A subject is considered registered when an 'On Study' date is entered into the EDC system.

Subjects must be registered prior to starting protocol therapy. Subjects must begin therapy within five business days of registration.

Blinding

This study treatment is not blinded to the subject or the investigator.

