Whole blood sample ¹⁴ - mandatory		Pre-dose			
BANKING STUDIES					
Whole Blood ¹⁵ – optional		Х			
Unstained Slides (diagnosis and surgery) ¹⁶ - optional		X			
Serum and Plasma ¹⁷ - optional		Х		X	
FOLLOW-UP					
Survival					Х

Footnotes:

1: Diagnosis and Staging to include pathology report and TNM staging

2: Vital signs to include temperature, blood pressure, pulse rate, respiratory rate, weight, and height (screen only).

3: ECGs are required during screening, pre and post treatment on C1D1, pre and post treatment at C4D1, end of treatment, and at any other time point when clinically indicated.

4: Cycle 1 Day 1 labs do not need to be repeated if done within 7 days prior to Day 1.

5: CBC with diff and platelets to include: hemoglobin, platelet count, red blood cell count, total white cell count.

6: CMP to include: albumin, alkaline phosphatase, alanine aminotransferase (ALT), aspartate aminotransferase (AST), bicarbonate, calcium, chloride, creatinine, gamma glutamyl transferase (GGT), glucose, lactate dehydrogenase (LDH), magnesium, potassium, sodium, total bilirubin, total protein, urea or blood urea nitrogen (depending on local practice), uric acid. If total bilirubin is $\geq 2xULN$ (and no evidence of Gilbert's syndrome), fractionate into direct and indirect bilirubin. GGT at baseline and as clinically indicated. Amylase and lipase will be checked at screening; amylase and/or lipase (depending on local practice) will be checked prior to Day 1 of each cycle.

7: Urinalysis performed at Screening, Day 1 of every cycle, and as clinically indicated. Urinalysis to include: bilirubin, blood, glucose, ketones, pH, protein, and specific gravity. Microscopy should be used as appropriate to investigate white blood cells and use the high power field for red blood cells.

8: Free T3 and free T4 will only be measured if screening TSH is abnormal. Free T3 and free T4 should also be measured if there is clinical suspicion of an adverse event related to the endocrine system.

9: Prothrombin time, aPTT and INR only performed at Screening and as clinically indicated.

10: Pregnancy test: Within 14 days of registration.

11: Disease assessment will be performed every 3 months \pm 7 days (prior to Cycle 4, 7, 10, etc.). During follow up, disease assessment will be performed every 3 months (\pm 7 days) for up to 1 year from the time of treatment discontinuation (if they have not withdrawn consent).

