7.6. Follow-up

Subjects can stop study participation at any time. All subjects without documented disease relapse will be followed every 3 months for 1 year from the time of treatment discontinuation (if they have not withdrawn consent) for assessment of survival, disease relapse, and occurrence of any late AEs.

- Physical exam and ECOG PS
- CT scan of the chest and abdomen/ pelvis every 3 months for up to 1 year from the time of treatment discontinuation (if they have not withdrawn consent).

Subjects will be off study after 1 year of follow-up from discontinuation of the study drug or at documented disease relapse, whichever comes first.

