8. CRITERIA FOR DISEASE EVALUATION

In some circumstances it may be difficult to distinguish disease recurrence and relapse from inflammatory findings. It is recommended that a repeat disease assessment be performed if needed to confirm disease relapse prior to taking a subject off study. The disease assessment should be performed no sooner than 4 weeks after the criteria for relapse is first met. During this interim period, subjects should continue to be followed per protocol, including continued dosing of the study drug.

8.1. Definitions for Disease Evaluation – RECIST version 1.1 [Eur J Ca 45:228-247, 2009]

8.1.1. Disease Relapse:

Any clinical or radiographic finding(s) that meet the criteria for measurable or nonmeasurable lesions (confirmed by histology/cytology if solitary) according to RECIST 1.1.

• If pseudoprogression is suspected, relapse will be confirmed by either a biopsy or repeat radiographic scans.

8.1.2. Overall Survival:

Overall Survival is defined by the date of registration to date of death from any cause.

8.1.3. Relapse Free Survival:

Time from the date of surgery until the criteria for disease relapse is met or death occurs.

8.2. Methods of Measurement

Both imaging-based evaluation and clinical examination will be used for assessment. The same imaging modality must be used throughout the study to measure disease. Baseline imaging should be available within 28 days of the first dose of study drug.

8.2.1. CT and MRI:

CT and MRI are the best currently available and most reproducible imaging methods for assessing solid organ malignancy. This guideline has defined measurability of lesions on CT scan based on the assumption that CT slice thickness is 5 mm or less. If CT scans have slice thickness greater than 5 mm, the minimum size for a measurable lesion should be twice the slice thickness. MRI is also acceptable in certain situations (e.g. for body scans).

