12.3. Definition of Primary Endpoint

- Relapse free survival: Time from the date of surgery until the criteria for disease relapse is met or death occurs.
- One year relapse free survival: Subject is alive and relapse free at one year post-surgery.

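### One-year RFS is read at one year from surgery, but no CT is tied to that date, so relapses silent at day 365 and found at the next scan count as successes

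*Combined protocol and SAP*

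**What the plan says.** Section 12.3 defines relapse-free survival as "Time from the date of surgery until the criteria for disease relapse is met or death occurs" and one-year success as "Subject is alive and relapse free at one year post-surgery". Section 8.1.1 defines relapse as "Any clinical or radiographic finding(s) that meet the criteria for measurable or nonmeasurable lesions" under RECIST 1.1, so a relapse is dated when it is detected.

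Scans run on other clocks:

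- **Entry.** Inclusion criterion 3.1.7 sets "Minimum of 1 month and maximum of 3 months from surgical resection", and Section 4 adds "Subjects must begin therapy within five business days of registration".
- **On treatment.** Section 7.2.2 gives "Every 3 months (prior to Cycle 4, 7, 10, etc.): CT of chest, abdomen and pelvis". Footnote 11 of the Section 7 calendar says "Disease assessment will be performed every 3 months", with a 7-day tolerance and the same cycle list.
- **Off treatment.** Section 7.6 gives CT "every 3 months for up to 1 year from the time of treatment discontinuation".

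No section places a CT at or near one year from surgery. Section 12.12 plans a one-year rate with a 95% confidence interval and a Kaplan-Meier curve. Section 12.1 rules out imputation. Neither sets an assessment window, a back-dating rule or an interval-censored analysis.

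**The concern.** The endpoint is status at a fixed date, but the main tool for establishing that status is not scheduled for that date. A relapse that is present but silent on day 365 and first seen at the next CT has a recorded RFS above one year, so the patient counts as a success. Relative to the true one-year rate this error goes one way, because a scan cannot find a relapse before it exists. Its size depends on the interval from surgery to Cycle 1, which has nothing to do with the drug. With a single arm, no concurrent control shares the delay and cancels it. The decision rule also has little slack, as shown in the working.

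**Working it through.** **Inputs from the documents.** Null 50%, alternative 75%, alpha 0.05, power 80%, 23 evaluable patients, 15 or fewer successes meaning no further study (Section 12.6); 28-day cycles (Section 7); entry at 1 to 3 months (3.1.7).

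**Assumptions.** Cycle 1 is spread evenly over days 30 to 91 after surgery; the hazard is constant from surgery; patients stay on the cycle rhythm. Scan-only detection is the upper bound. Three 28-day cycles make 84 days, whereas three months is about 91, so both spacings are shown.

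**1. The plan's own figures.** By exact binomial, P(X ≥ 16 | n = 23, p = 0.50) = 0.0466 and P(X ≥ 16 | n = 23, p = 0.75) = 0.8037. No smaller n reaches 80% power with one-sided alpha at or below 0.05, so 23 reproduces. The half-width at n = 34 is 1.96 × √(0.75 × 0.25 / 34) = 0.1455, stated as 15%.

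**2. Where scans fall.** Scan day = s + d × k, where s is the day of Cycle 1, d is the spacing and k counts scans. L is the last scan on or before day 365; the gap is 365 − L.

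| Cycle 1 (s) | Spacing (d) | Last scan (L) | Next scan | Gap |
|---|---|---|---|---|
| 30 | 84 | 282 | 366 | 83 |
| 60 | 84 | 312 | 396 | 53 |
| 91 | 84 | 343 | 427 | 22 |
| 30 | 91 | 303 | 394 | 62 |
| 60 | 91 | 333 | 424 | 32 |
| 91 | 91 | 364 | 455 | 1 |

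Over s = 30 to 91, the mean gap is 52.5 days at 84-day spacing and 31.5 days at 91-day spacing.

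**3. Upper bound on the recorded rate.** With scan-only detection, the recorded rate is p^(L/365). For s = 60 and d = 84 at a true 50%, 0.5^(312/365) = 0.553. Averaged over s:

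| True rate | 84-day | Excess | 91-day | Excess |
|---|---|---|---|---|
| 50% | 55.3% | 5.3 points | 53.1% | 3.1 points |
| 75% | 78.2% | 3.2 points | 76.9% | 1.9 points |

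Allowing the five business days to first dose (s up to 98) changes little: at a true 50% the recorded rate is 54.9% or 53.6%.

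**4. Partly silent events.** If a fraction f of gap events is silent, the recorded rate is p + f × (upper bound − p). For f = 0.5 at a true 50%, this is 0.50 + 0.5 × 0.0527 = 0.526 (84-day) or 0.50 + 0.5 × 0.0311 = 0.516 (91-day), an excess of 2.6 or 1.6 points.

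**5. Effect on the 23-patient rule, only if the historical 50% carries no detection lag.** P(X ≥ 16 | 23) at a true 50%:

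| Silent fraction | 84-day | 91-day |
|---|---|---|
| none | 0.047 | 0.047 |
| a quarter | 0.060 | 0.054 |
| half | 0.077 | 0.063 |
| all (upper bound) | 0.120 | 0.084 |

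**The case against.** A reader might infer that the trial's type I error is inflated, to as much as 0.12. The documents do not support that as a finding. The 50% in Section 12.6 is an observed historical figure, and any follow-up cohort also dates relapse by detection. The documents do not say how often that cohort was scanned. If its lag was similar, the error against the benchmark largely cancels; if its scans were sparser, 3-monthly CT here could work against the drug. The error rates in step 5 are therefore conditional. They also apply only to the 23-patient rule: Section 12.6 justifies 34 patients by precision and gives no cut-off for that number.

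The upper bound is also a worst case. Deaths are RFS events with no scan delay, clinical findings count as relapse, and Section 2.3.1 has examinations every 4 weeks on drug. At a true 75% the excess is at most 3.2 points, against a stated half-width of 15. Dating relapse by detection on 3-monthly scans is common practice. CT continues after treatment stops, so the first scan after day 365 will normally exist, and Section 12.1 already allows extra exploratory analyses.

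All of this limits the size of the problem. It does not remove the mismatch: the endpoint is status at one year from surgery, and no planned scan is tied to that date.

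**Conclusion.** The point holds as a gap in how the endpoint is ascertained, with a modest effect. The recorded one-year rate exceeds the true one by an amount set partly by the surgery-to-start interval. At a true 50% the average excess is at most 5.3 points (84-day spacing) or 3.1 (91-day), and about 1.6 to 2.6 points if half of the gap events are silent. At a true 75% it is at most 3.2 or 1.9 points. These sizes rest on constant hazard, an even spread of start days and patients staying on cycle; for early stoppers the gap depends on the discontinuation date.

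Any rise in the chance of 16 or more successes in 23 (to 0.063–0.077 with half silent, at most 0.084–0.120) further assumes a lag-free historical 50%, which the documents do not show. The sample size of 23 is not in question. The change is worth making because it is cheap and lets the primary endpoint be measured as defined.

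**What to change.** 1. **Section 7, calendar footnote 11, and Section 7.6:** move one of the planned 3-monthly CTs to 12 months from surgery with a stated window, for example day 365 ± 14, including for patients who stopped treatment early.
2. **Sections 12.3 and 12.12:** base one-year status on that assessment, and count a relapse first documented at it as a one-year failure. Without this rule, even a scan on day 366 would turn a relapse found there into a success.
3. **Section 12.12:** add an interval-censored estimate of one-year RFS as a sensitivity analysis. It needs no further data.

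Under the same constant-hazard, scan-only model, a 14-day window leaves an error of at most about 1.3 points either way at a true 50%: 0.5^(351/365) = 0.513 and 0.5^(379/365) = 0.487.

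The cost is a footnote and a few sentences in the analysis section. No scan or patient is added, and dosing is untouched. The downsides are one scan off the cycle rhythm, a slightly lower reported rate, and a few relapses arising late in the window counted as failures. Comparability with the historical rate may also fall if that rate was dated by detection without a landmark scan, so the report should say how the historical figure was obtained.
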